## 2. SYNOPSIS

Protocol Number XSGP-302	
A PHASE 3 STUDY TO EVALUATE THE GLUCOSE RESPONSE OF G-PEN™ (GLUCAGON INJECTION) IN PEDIATRIC PATIENTS WITH TYPE 1 DIABETES	
Principal Investigator:	Each participating clinical site will nominate a physician who, based on training and experience, will serve as principal investigator for that site.
IND:	115091
Project phase:	Phase 3
Compound(s):	G-Pen™ (glucagon injection)
Objectives:	
The primary objective of this study is to assess the increase in plasma glucose from baseline to 30 minutes in subjects in a low normal glycemic state after injection of an age-appropriate dose of G-Pen™ (glucagon injection), in each of three age groups (2.0-<6.0 years, 6.0-<12.0 years and 12.0-<18.0 years) of pediatric patients with type 1 diabetes mellitus (T1D).
 
Secondary objectives of this study include:
 

1. In the 12-<18 year-old age group, to additionally assess the plasma glucose change from baseline to 30 minutes after administration of G-Pen™ (glucagon injection) at a dose of 0.5 mg.

2. Determine G-Pen™ (glucagon injection) pharmacokinetics for each age group, and

3. Determine the safety and tolerability of G-Pen™ (glucagon injection) for each age group.

Study design:	
This is a sequential efficacy and safety study in pediatric patients with T1D. Subjects using insulin injections will be administered IV insulin and subjects using an insulin pump will have the basal rate increased to induce a low normal glycemic state and will then receive an age-appropriate dose of G-Pen™ (glucagon injection) in a clinical research center (CRC) or comparable setting.
 
Subjects ages 2-<12 will complete a single treatment visit and will receive a 0.5 mg dose of G-Pen™. Subjects ages 12-<18 will receive a 1 mg dose of G-Pen™ at an initial treatment visit, and will be given the 0.5 mg dose at a second visit occurring 7-28 days later.

Study location:	Approximately 8 US-based pediatric clinics.
Study duration:	Estimated duration of study participation for individual subjects is approximately 2-6 weeks. Estimated duration of the study is 5 months.

Sample size:	Approximately 48 subjects are anticipated to be screened for this study, and approximately 24 (up to 8 per cohort) will receive study drug to achieve the goal of 18 evaluable subjects equally distributed (n=6 per cohort) across the three age groups: 2.0-<6.0, 6.0-<12.0 and 12.0-<18.0 years.
Subjects:	Male or female patients with T1D ages 2.0-<18.0 years, inclusive.
Inclusion Criteria:	
 
1. Males or females diagnosed with T1D for at least 6 months at Screening.
 
2. Current usage of daily insulin treatment.
 
3. Age 2.0 <18.0 years, provided that subject will be <18.0 years for the duration of the study.
 
4. Willingness of subject and adult guardian to follow all study procedures, including attending all clinic visits.
 
5. Parent or guardian has provided written informed consent and assent has been obtained from subjects if appropriate for age according to IRB requirements.
 

Exclusion Criteria:	
 
1. Pregnant and/or Nursing: For subjects of childbearing potential, there is a requirement for a negative urine pregnancy test and for agreement to use contraception and to refrain from breast feeding during the study and for at least 1 month after participating in the study. Acceptable contraception includes birth control pill / patch / vaginal ring, Depo-Provera, Norplant, an IUD, the double barrier method (the female uses a diaphragm and spermicide and the male uses a condom), or abstinence.
 
2. Renal insufficiency (serum creatinine of <math>\geq 1.5</math> mg/dL [males], <math>\geq 1.4</math> mg/dL [females]).
 
3. Serum ALT or AST equal to or greater than 3 times the upper limit of normal
 
4. Hepatic synthetic insufficiency as defined as a serum albumin of less than 3.0 g/dL; or serum bilirubin of over 2.0 mg/dL.
 
5. Hematocrit of less than or equal to 30%.
 
6. Mean of triplicate BP readings at Screening where SBP or DBP >95% of normal for age and height percentile.
 
7. Use of > 2.0 U/kg total insulin dose per day.
 
8. Inadequate venous access.
 
9. Current seizure disorder.
 
10. History of pheochromocytoma or disorder with increased risk of pheochromocytoma (MEN 2, neurofibromatosis, or Von Hippel-Lindau disease).
 
11. History of insulinoma.
 
12. History of allergies to glucagon or glucagon-like products, or any history of significant hypersensitivity to glucagon or any related products or to any of the excipients (DMSO & trehalose) in the investigational formulation.
 
13. History of glycogen storage disease.
 
14. Any concurrent illness, other than diabetes, that is not controlled by a stable therapeutic regimen.
 

	
15. Active use of alcohol or drugs of abuse.
 
16. Administration of glucagon within 14 days of the first treatment visit.
 
17. Participation in other studies involving administration of an investigational drug or device within 30 days or 5 half-lives, whichever is longer, before screening for the current study and during participation in the current study.
 
18. Any reason the principal investigator deems exclusionary.


Brief outline of treatments:
	
Subjects will complete the screening procedures up to 30 days before dosing to determine eligibility before enrollment in the treatment phase.
 
For treatment visits, subjects will arrive at the clinical center in the morning, having fasted for at least 8 hours prior to dosing.
 
The following procedures will be performed:
 

• The glucose level will be checked:

○ If >300 mg/dL, ketones will be checked.

○ If ketones are found to be moderate or greater, the visit will be postponed.

• Assessment of any severe hypoglycemic events (requiring the assistance of another person) since the screening visit:

○ If a severe hypoglycemic event has occurred in the 2 weeks prior to the admission, the visit will be postponed until it has been at least 2 weeks since the last severe hypoglycemic event.

• For females of child-bearing potential, a urine pregnancy test will be performed:

○ If positive, the subject will be discontinued from the study.

• Insertion of intravenous catheter for blood sampling:

○ Those subjects using injection therapy will have a second intravenous catheter inserted in the other arm for insulin infusion.

 
Procedures for Insulin Infusion
 
Insulin Pump Users: At the start of the test, the basal insulin rate will be increased by approximately 25-50% to provide a gradual decline in blood glucose. A small priming bolus dose of insulin equal to approximately one hour of the subject's usual basal dose may also be given at the discretion of the investigator in addition to the 25-50% increase in the basal insulin.
 

• The basal insulin rate may be increased an additional amount and additional bolus insulin doses may be given at the discretion of the investigator in order to get a gradual decline in glucose concentration.

 
Insulin Injection Users: If the starting glucose level is >200 mg/dL, a priming dose of 2-4 units of IV insulin may be given. An intravenous infusion of regular insulin diluted in normal saline at a rate of 1 mU/kg/min will be administered. The infusion rate will be adjusted as necessary to reach the target glucose level of <80 mg/dL.

	
For Both Pump and Injection Users: For all subjects, plasma glucose levels will be measured using a bedside rapid glucose analyzer (Analox, YSI or equivalent). During the insulin infusion, glucose levels will be measured no more than 10 minutes apart while the plasma glucose level is <math>\geq 100</math> mg/dL and no more than 5 minutes apart when the plasma glucose level is <math>< 100</math> mg/dL.
 
Once a plasma glucose level of <math>< 80</math> mg/dL is reached, the basal rate will be returned to normal for subjects using an insulin pump and the insulin infusion will be stopped for subjects using insulin injections.
 
If the starting plasma glucose is <math>< 80</math> mg/dL, no additional insulin will be given and the procedures below will be followed.
 
Dosing with glucagon will be at 5 minutes following a measurement of plasma glucose <math>< 80</math> mg/dL. Subjects will receive a subcutaneous injection of G-Pen™ glucagon at an age appropriate dose (0.5 mg for 2-<math>< 12</math> years, 0.5 or 1.0 mg for 12-<math>< 18</math> years).
 
Plasma glucose will be measured at bedside at -5 and 0 minutes, and every 5 minutes for 90 minutes after dosing. In addition, blood samples will be collected at -5, 0, 10, 20, 30, 45, 60, 90, 120, and 180 minutes and stored at <math>-80 \pm 20</math> C for determination of plasma glucagon concentration. Body weight may limit the number of blood draws (see below).
 
After this, the subject will be given a meal and will receive insulin according to her or his normal dosing regimen. The subject can then leave the clinic.
 
Tolerability will be assessed by comparing adverse event reports between the groups. Subjects will also complete age-appropriate questionnaires concerning injection site discomfort. In addition, modified Draize scales will be used by an investigator to evaluate the injection site at 10, 30 and 180 minutes following administration, as appropriate.
 
Volume of Blood Draws
 
The maximum blood volume to be collected will not exceed 5% of the subject's blood volume. The number of blood draws will be reduced for subjects who do not weigh enough to allow for the full schedule to be completed. Early collections (-5 to 30 minutes) will be preferred over later blood draws, and Pharmacodynamics samples will be prioritized over Pharmacokinetic samples.


Data management and statistical analysis:
	
Data will be entered from the source (e.g Case Report Forms) into Advantage eClinical an Electronic Database Capture (EDC) system by site personnel. Data will be monitored remotely and at on-site visits by the Clinical Research Associate (CRA).
 
Both primary and secondary endpoints will be summarized descriptively within each of the 3 age groups. Mean, standard deviation, median, minimum and maximum will be presented for continuous variables. Count and percentage variables will be presented for discrete variables. The primary endpoint will also be compared to 0 change using a simple t-test.
 
Pharmacokinetic data will be analyzed descriptively by dose/age cohort.

Sample Size Determination:
	
Based on results of a prior study, G-Pen™ (glucagon injection) is expected to increase glucose by minimally 25 mg/dL from baseline within 30 minutes of administration in every subject. Assuming a standard deviation of 18 mg/dL, a

sample size of 6 subjects per cohort has been chosen to provide 90% power to detect an increase of plasma glucose from baseline to 30 minutes after treatment.

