## **13. DATA ANALYSIS AND STATISTICAL METHODS**

### **13.1. Sample Size Determination**

In Phase 2 study XSGP-201, healthy normal adults were dosed with G-Pen™ after an overnight fast with baseline plasma glucose values that were similar to the target (< 80 mg/dL) planned for this study. The mean increase in glucose at 30 minutes post-dosing was approximately 35 mg/dL (SD = 18). Based on these findings, a sample size of 6 subjects per cohort has been chosen to provide 90% power to detect an increase of plasma glucose from baseline to 30 minutes after treatment, assuming a type 1 error rate of 5%.

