1.2 Endpoints

1.2.1 Primary Endpoints

The primary endpoint for this study is an evaluation of the change in plasma glucose following treatment with G-Pen™ (glucagon injection), particularly to quantify the increase from baseline to 30 minutes post-dosing, in each of three age groups.

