1.3 Sample Size

In the Phase 2 study XSGP-201, healthy normal adults were treated using the G-Pen™ after subject completed an overnight fast and presented with baseline plasma glucose values similar to the target levels (< 80 mg/dL) planned for this study. The mean increase in glucose at 30 minutes post-dosing was approximately 25 mg/dL (standard deviation = 18). Based on these assumptions, a sample size of 6 subjects per age group is required to provide 90% power to detect at least this change in the primary endpoint, i.e., an increase of plasma glucose from baseline to 30 minutes after treatment, assuming a type 1 error rate of 5%.

Therefore, approximately forty-eight subjects are anticipated to be screened for this study, and 36 (up to 12 per age group) will be enrolled and receive study treatment to achieve the goal of 18 evaluable subjects equally distributed (n=6 per age group) across the three age groups: 2.0-<6.0, 6.0-<12.0, and 12.0-<18.0 years old. Each age group is an independent clinical experiment with its own α -level of 0.05.

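### The synopsis states the sizing assumption as a 25 mg/dL rise in every child, which fits neither prior-study mean given elsewhere (35 or 25), and the primary tables lack an interval and a 30-minute count at 25 mg/dL

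*Protocol*

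**What the plan says.** The synopsis gives the sizing rationale as an individual minimum: the product "is expected to increase glucose by minimally 25 mg/dL from baseline within 30 minutes of administration in every subject". The next sentence begins "Assuming a standard deviation of 18 mg/dL" and concludes that a "sample size of 6 subjects per cohort has been chosen to provide 90% power to detect an increase of plasma glucose from baseline". It gives no mean rise and does not name the prior study.

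Protocol 13.1 reaches the same six from a mean in study XSGP-201: "The mean increase in glucose at 30 minutes post-dosing was approximately 35 mg/dL (SD = 18"). SAP 1.3 cites the same study and the same SD with another mean: "The mean increase in glucose at 30 minutes post-dosing was approximately 25 mg/dL (standard deviation = 18"). Both use a type 1 error of 5%. Only SAP 2.3.1 says that the tests are two-sided.

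For the analysis, the synopsis says: "The primary endpoint will also be compared to 0 change using a simple t-test". Protocol 13.2.1 and SAP 2.3.1 repeat this within each age group, in addition to the descriptive summary. SAP Table 7, and Table 8 for the 0.5 mg visit in ages 12 to <18, show mean, SD, median, minimum and maximum at baseline, at 30 minutes and for the change, with a p-value against zero. SAP 1.2.1 describes the primary endpoint as an evaluation of the glucose change, "particularly to quantify the increase from baseline to 30 minutes post-dosing, in each of three age groups".

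The 25 mg/dL figure returns as a descriptive secondary endpoint, the time to a rise of that size (protocol 13.2.3, SAP 2.4.2, Tables 9 and 10).

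**The concern.** The sizing basis appears in three forms: a floor of 25 for each child, a mean of 35 and a mean of 25. A floor and a mean are different quantities. With an SD of 18, many children lie below a mean of 25, and a sizeable minority lie below 25 even when the mean is 35. The planned test reaches its stated power at one of the two means and not at the other.

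The second issue is what the primary tables let a reader conclude. Each age group stands alone with about six evaluable children, and the proposed indication is severe hypoglycemia. The precision of the mean rise and the number of children with a weak response at 30 minutes are therefore the natural questions. Tables 7 and 8 print neither.

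**Working it through.** **Inputs.** n=6 per group and target power 90% (synopsis, protocol 13.1, SAP 1.3); SD 18 (all three); mean rise 35 (protocol 13.1) or 25 (SAP 1.3); alpha 0.05, two-sided (SAP 2.3.1); null value 0 (protocol 13.2.1, SAP Table 7).

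**1. Reproducing six.** The one-sample normal formula is n = [SD × (z0.975 + z0.90) / mean]².
- Mean 25: [18 × (1.960 + 1.282) / 25]² = 5.45, rounded up to 6.
- Mean 35: 2.78, rounded up to 3.

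So six follows from a mean of 25 by the normal approximation. It also follows from a mean of 35 by the t-test, as step 2 shows.

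**2. Power of the planned test.** This uses the two-sided noncentral t, with noncentrality (mean/SD) × √n.

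| True mean | Power at n=6 | Smallest n for 90% |
|---|---|---|
| 35 | 96.3% | 6 (n=5 gives 89.4%) |
| 25 | 77.5% | 8 (91.8%) |

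At mean 25, a one-sided t-test at n=6 would give 89.6%, but the SAP specifies two-sided tests.

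**3. Share of children below 25 mg/dL at 30 minutes.** With normal changes and SD 18, P(change < 25) = Φ((25 − mean)/18).
- Mean 35: 28.9%. All six reach 25 with probability (1 − 0.289)⁶ = 12.9%.
- Mean 25: 50%. All six reach 25 with probability 0.5⁶ = 1.6%.

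For a 90% chance that all six reach 25, the mean would have to be about 63. One part needs no normality: if 25 were both the minimum and the mean of the 30-minute change, the SD would be 0, not 18.

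**4. What p<0.05 requires.** The smallest significant mean is t(0.975, n−1) × SD/√n. At n=6 and observed SD 18 it is 2.571 × 18/√6 = 18.9 mg/dL, which is also the half-width of the 95% interval. At n=8 it is 15.0, and at n=12 it is 11.4.

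Changes of 0, 0, 35, 35, 35, 35 give mean 23.3, SD 18.1, t = 3.16 and p = 0.025. With three zeros and three at 35, p = 0.076. If two children are fixed at zero and four are drawn from a normal distribution with mean 35, simulation gives significance in 94% of cohorts at SD 10 and in 53% at SD 18.

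**5. What the existing 25 mg/dL endpoint supplies.**
- It is read from a profile that runs to 90 minutes, so it does not isolate the 30-minute point.
- SAP 2.4.2 defines no value for a child who never reaches 25.
- SAP 3.2 drops a subject from the PD analysis if an early glucose-elevating intervention censors more than half of the glucose values. There are 90/5 = 18 scheduled post-dose readings, so on those readings this means an intervention before the 45-minute reading.
- For the primary analysis, SAP 3.2 keeps such a child, using the last value before the intervention. A count built on the primary-analysis value would therefore keep the children that Tables 9 and 10 can lose.

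**The case against.** **The wording is an expectation, not a criterion.** The synopsis sentence sits in a sample-size rationale. The objective is to assess the increase, the summaries are descriptive, and the t-test supplements them. This stands. A reader might infer that a cohort succeeds with a mean rise of 19 mg/dL, or with a third of its children not responding. The documents define no success rule and no 25 mg/dL benchmark; p<0.05 is simply the only test result they produce.

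**A floor of 25 and an SD of 18 can coexist.** This is true for a right-skewed distribution. For example, about 76% of children at 25 and 24% at 67.4 gives mean 35 and SD 18. The synopsis also says within 30 minutes, so a child could reach 25 earlier and be lower at 30. It would therefore be too strong to say that the SD alone contradicts the floor. The 29% and 50% rest on normality, on a mean taken from another section and on the 30-minute value.

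**The 25 mg/dL threshold is already an endpoint, and Table 7 prints the minimum change.** Both are true. It would be wrong to say that the threshold disappears or that a non-responder would be hidden: with two children at zero, Table 7 shows a minimum of 0. It does not show how many children are low, and Tables 9 and 10 have the limits listed in step 5.

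**The interval can be worked out from mean, SD and N.** It can, so adding it is a reporting improvement and supplies no new information.

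**The example with two zeros is chosen.** It is possible rather than expected. Under the normal model with mean 35 and SD 18, two or more of six children with no rise has a probability of about 1%.

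**Conclusion.** Two limited points hold.

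First, the sizing basis is inconsistent. A floor of 25 for each child fits neither stated mean under a normal model with SD 18 (29% below at mean 35, 50% below at mean 25), and the two means for XSGP-201 differ. The consequence is concrete: the planned two-sided t-test at n=6 has 96% power if 35 is right and 77.5%, not 90%, if 25 is right. A general statement that the trial is underpowered is not supported, because at mean 35 six is the smallest number that reaches 90%.

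Second, the primary tables give no interval for the mean change and no count at 25 mg/dL at 30 minutes, and the time-to-25 summaries do not replace that count. The 18.9 mg/dL figure assumes six children analysed and an observed SD of 18. It shows how little a p-value against zero says about the size of the rise. It is not a flaw in testing against zero.

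**What to change.** **1. Sizing text.** In the synopsis, replace the per-child minimum with a mean-rise assumption. Use the same mean in the synopsis, protocol 13.1 and SAP 1.3, after checking it against the XSGP-201 results. State the sidedness and the power of the planned t-test at n=6: 96% for a mean of 35, 77.5% for a mean of 25. If 25 is the right mean, the 90% claim has to go, or the evaluable target has to be eight.

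**2. SAP Tables 7 and 8.** For each age group and dose, add (a) the 95% t confidence interval for the mean change and (b) a descriptive n/N with a change of at least 25 mg/dL at 30 minutes, with an exact 95% interval. Use the value that enters the primary analysis, including the replacement and carry-forward rules in SAP 3.2 and 3.3.

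Keep the test against zero and do not turn 25 mg/dL into a success criterion. With 25 as the null value, power at n=6 and a true mean of 35 would be about 20%, and 90% would need 37 children per group.

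**Cost.** Wording changes and two added columns, with no new data. The intervals will be wide: about ±19 mg/dL for the mean at n=6 and SD 18, a lower bound of 54% for 6/6, and 22% to 96% for 4/6.

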#### 4. LIST OF ABBREVIATIONS AND DEFINITIONS OF TERMS

The following abbreviations and specialist terms are used in this study protocol.

**Table 2: Abbreviations and Specialist Terms**

AE	Adverse Event
ALT	Alanine Aminotransferase
AST	Aspartate Aminotransferase
AUC	Area Under the Curve
BP	Blood Pressure
CLIA	Clinical Laboratory Improvement Act
C max	Maximum Plasma Concentration
CGM	Continuous Glucose Monitor
CRF	Case Report Form
CRC	Clinical Research Center
CRO	Contract Research Organization
DMSO	Dimethyl sulfoxide
ECG	Electrocardiogram
GCP	Good Clinical Practice
HbA1c	Glycated hemoglobin
HBV	Hepatitis B virus
HCV	Hepatitis C virus
HIV	Human immunodeficiency virus
HR	Heart Rate
ICF	Informed Consent Form
IB	Investigator's Brochure
ICH	International Conference on Harmonization

IEC	Independent Ethics Committee
im	Intramuscular
IRB	Institutional Review Board
IUD	Intra-uterine device
iv	Intravenous
kg	Kilogram
L	Liters
LSLV	Last Subject Last Visit
MedDRA	Medical Dictionary for Regulatory Activities
mg	Milligram
min	Minute
mmHg	Millimeters Mercury
NOAEL	No Observed Adverse Effect Level
PD	Pharmacodynamics
PK	Pharmacokinetic
RBC	Red blood cells
rDNA	Recombinant
RLD	Reference Listed Drug
SAE	Serious Adverse Event
sc	Subcutaneous
THC	Tetrahydrocannabinol
Tmax	Time to Maximum Plasma Concentration
T1D	Type 1 Diabetes Mellitus
ULN	Upper Limit of Normal

VAS	Visual Analog Scale
WHO	World Health Organization
YSI	Yellow Springs Instrument

## 5. STUDY OBJECTIVES AND ENDPOINTS

### 5.1. Primary Objective

The primary objective of this study is to assess the increase in plasma glucose of subjects from baseline to 30 minutes in subjects in a low normal glycemic state after injection of an age-appropriate dose of G-Pen™ (glucagon injection), in each of three age groups (2.0-<6.0 years, 6.0-<12.0 years and 12.0-<18.0 years) of pediatric patients with type 1 diabetes mellitus (T1D).

### 5.2. Secondary Objectives

The secondary objectives of this study are:

- In the 12-<18 year-old age group, to additionally assess the plasma glucose change from baseline to 30 minutes after administration of G-Pen™ (glucagon injection) at a dose of 0.5 mg.
- Determine G-Pen™ (glucagon injection) pharmacokinetics for each age group.
- Determine the safety and tolerability of G-Pen™ (glucagon injection) for each age group.

